Opioids were the most frequently used method to control orthopedic pain. However, multiple complications has been encountered with the use of opioids in elderly patients such as delirium, hypotension, respiratory depression, prolonged hospital stay or post-discharge side effects as addiction or dependence ^[7]. Fentanyl can be considered the most suitable among different opioids due to its potency, rapid onset, short duration and minimal depressive effect on respiration ^[8].

Regional nerve blocks can efficiently reduce pain associated with hip fracture, with rapid-onset, site-specific analgesia that is more effective than standard systemic analgesia alone. There is also moderate evidence that nerve blocks contribute to reduce rates of delirium, and some suggestion of reduced length of inpatient stay, morbidity and mortality^[9]. Therefore, regional analgesia provides a safer alternative for opioids with even stronger analgesia and fewer complications. The use of regional analgesia is not limited to operation room (O.R), it can be started from the emergency department to facilitate patient examination, transportation and radiological investigations ^[10].

With ultrasound guidance, regional analgesia became easier, more accurate, more specific and requires less amounts of local anesthetic. Regional analgesia for hip fractures was strongly recommended by both pain management pathway by Health Quality Ontario ^[11] and by the evidence based guidelines published by the American Pain Society, the American Society of Regional Anesthesia and Pain Medicine and the American Society of anesthesiologists ^[12].

There is multiple techniques to provide analgesia for hip fractures through peripheral nerve block while patient in supine position including femoral nerve block, 3-in-1 block, fascia iliaca block, intraarticular injections and local anesthetic infiltration in soft tissues surrounding surgical site (the last is suitable for postoperative pain) ^[13].

One method widely used to provide regional analgesia for hip fractures is ultrasound guided Fascia Iliaca block in which local anesthetic is injected between fascia iliaca and psoas muscle to block femoral, obturator and lateral cutaneous nerves ^[14].

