There is a difference between ultrasound guided Pericapsular Nerve Group Block and ultrasound guided Fascia Iliaca Block as a regional analgesic techniques for pre- and post-operative analgesia in elderly patients with hip fracture.

Aim of the work

The aim of the present study is to improve quality of pain control in the pre- and post-operative periods in elderly patients with hip fracture.

Objectives

1. To compare the time of performance and the analgesic effect in the pre- and post-operative periods between ultrasound guided Pericapsular Nerve Group (PENG) block, fascia iliaca block and intravenous fentanyl (control group).
2. To assess the quality of patient's positioning during performance of spinal anesthesia by operator satisfaction score.
3. To assess time of onset of postoperative ambulation.

Patients and Methods

I. Technical design:

● **Site of the study:**

This study will take place at Zagazig University Hospitals after approval of Institutional Review Board (IRB).

● **Duration of the study:**

Two years.

● **Sample size:**

Assuming that mean \pm SD for VAS scores at positioning for spinal anesthesia in intravenous fentanyl versus fascia iliaca block were 3.5 ± 2.5 versus 2.1 ± 0.9 [4] with confidence level 95% and power of test 80%.

The total sample size is 51 (17 in each group) calculated by OpenEpi[®].

● **Inclusion criteria:**

1. Patient acceptance.
2. Accepted mental state of the patient.
3. Gender: both sexes.
4. Age above 65 years old.
5. Body mass index 18.5-35 kg/m².
6. ASA physical status II and III.
7. Unilateral hip fracture assigned for surgical fixation.
8. Expected duration of surgery \leq 3 hours.

● **Exclusion criteria:**

1. Associated trauma or multiple fractures.
2. Peripheral neuropathy.
3. Coagulopathy.
4. Infection at site of injection.
5. Allergy to the drugs used in the study.
6. Advanced kidney, liver or heart disease.

- **Withdrawal criteria:**

The patient has the right to withdraw from the study at any time without any negative consequences on their medical or surgical treatment plan.

II. Operational design:

- **Type of the study:**

This study is a randomized double-blind controlled clinical trial.

- **Parameters of the study:**

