Patient will be evaluated for the effect of spinal block regarding both sensory and motor blocks. Sensory level will be evaluated using pin prick. Motor block will be evaluated using the modified bromage scale. Patient is asked to elevate his extended lower limbs and the score is given as follows: ^[19]

Grade 0 = No motor block.

Grade 1 = Inability to raise extended leg; able to move knees and feet.

Grade 2 = Inability to raise extended leg and move knee; able to move feet.

Grade 3 = Complete motor block of the limb.

The surgery will be started after achieving grade 3 on modified bromage scale and sensory level reaching umbilicus (T10). Patients will be monitored for heart rate (HR), oxygen saturation (SpO₂), mean arterial blood pressure (MAP) and body temperature and recorded every 10 minutes till the end of operation. Patients will be also monitored for the possible side effects of the used techniques (spinal anesthesia, regional blocks and parenteral fentanyl).

- Possible complications of spinal anesthesia include hypotension (decrease in systolic blood pressure by >20% of basal value) and bradycardia (decrease in heart rate by >20% of the basal value). Hypotension will be treated by intravenous fluids and vasopressor (ephedrine bolus 5mg repeated after 3 minutes if needed) while bradycardia will be treated by 1 mg of atropine.
- The most feared complication of regional blocks is local anesthetic toxicity. It can be avoided by not exceeding the toxic dose (2-2.5 mg/kg for bupivacaine) and avoiding inadvertent intra-arterial injection by proper visualization of the needle and injected local anesthetic by ultrasound and aspiration test before every increment injection. Manifestations of toxicity includes tingling of the tongue, circumoral numbness, tinnitus, blurred vision, agitation, muscle twitches, convulsions and cardiovascular manifestations as hypotension, bradycardia, heart block and cardiac arrest. Treatment is mainly supportive (respiratory and cardiovascular support), cardiopulmonary

resuscitation in case of cardiac arrest and the antidote is intralipid 20% (1.5 ml/kg over 1 minute then infusion in a rate of 0.25 ml/kg/min).

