- In the elderly parenteral fentanyl may cause delirium or respiratory depression. Delirium can be assessed using the confusion assessment method (CAM). The CAM diagnostic algorithm is based on four cardinal features of delirium: 1) acute onset and fluctuating course, 2) inattention, 3) disorganized thinking, and 4) altered level of consciousness. A diagnosis of delirium according to the CAM requires the presence of features 1, 2, and either 3 or 4 [20].

At the end of the procedure patient will be asked to evaluate the analgesic technique used by patient's satisfaction score: Patient will be asked to rate his satisfaction with the technique of analgesia used by giving a score on a 1-3 scale (1 = unsatisfactory analgesia, 2 = satisfactory analgesia, 3 = excellent analgesia) [21].

In the recovery room: Patient will receive 1 gm paracetamol and 30 mg ketorolac by intravenous infusion as a part of standard multimodal analgesia.

In the ward: Postoperative standard analgesia will continue in the form of 1gm paracetamol/8hours and ketorolac 30 mg/12hours. Patient will be monitored for vital signs (HR, MAP, SpO₂ and body temperature), time of offset of spinal anesthesia (time from end of intrathecal injection of hyperbaric bupivacaine till recovery of the lower limbs motor power indicated by achieving grade 0 on modified bromage scale and fine touch sensation indicated by sensing pin brick) and postoperative pain by VAS score. Vital signs and VAS will be recorded at 2, 4, 6, 12 and 24 hours postoperative.

If patient gives VAS \geq 4 or complains of intolerable pain, a rescue analgesia will be given in the form of nalbuphine 0.1 mg/kg. We will record time of first rescue analgesia (the time between complete injection of the local anesthetic in the regional groups or fentanyl injection and the first analgesia requested by the patient), total postoperative rescue analgesic consumption in first 24 hours and time of onset of postoperative ambulation.

• **Collecting data:**

From each patient the following data will be collected:

- Patient characteristics (name, age, gender, body mass index (BMI), ASA grade).
- Fracture type.
- Type and duration of surgery (time from end of skin preparation till suturing the wound).

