- Physical examination (mental status, decubitus, chest, abdomen, neurological and examination of the site of injection), laboratory investigations (complete blood count, random blood sugar, international normalized ratio, prothrombin time, partial thromboplastin time, kidney functions tests, liver functions tests and serum electrolytes).
- Vital signs (heart rate, mean blood pressure, respiratory rate, temperature and SpO₂). Vital signs will be recorded before and after the analgesic technique, during positioning for spinal anesthesia and then every 10 minutes till the end of the surgery. Then we will record vital signs at 2, 4, 6, 12 and 24 hours postoperative.
- Intraoperative total fluids given, blood loss and urine output.
- Visual analogue pain score will be recorded before and after analgesic technique used (starting 10 minutes after regional blocks and repeated every minute and 2 minutes after fentanyl injection) and during positioning. VAS will be also recorded at 2, 4, 6, 12 and 24 hours postoperative.
- Time of block performance (time from the end of skin sterilization till end of injection of local anesthetic).
- Onset time of the analgesic technique (time from end of injection of local anesthetic or intravenous fentanyl till reaching VAS \leq 4) by 15 degrees leg raising test. The 15 degrees leg raising test will be used after 10 minutes in the groups received regional analgesia and 2 minutes in the fentanyl group. We will try to elevate the patient's leg for 15 degrees. If the patient complains of pain on moving his leg, the test will be aborted and we will wait for a minute before repeating the test.
- Patient's satisfaction score.
- Anesthesiologist satisfaction score for patient's positioning.
- Possible complications of spinal anesthesia, regional blocks and parenteral fentanyl.

- Time of first rescue analgesia (the time between complete injection of the local anesthetic in the regional groups or fentanyl injection and the first analgesia requested by the patient) and total postoperative rescue analgesic consumption in first 24 hours postoperative.
- Time of onset of postoperative ambulation (time from end of surgery till first ambulation by the patient).
- Duration of spinal anesthesia (time from end of injection of intrathecal hyperbaric bupivacaine till offset of spinal anesthesia effect detected by degree 0 on modified bromage score and return of fine touch detected by sensing pin bricks).

- **Statistical analysis:**

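### Spinal duration is read in the lower limbs without excluding the operated one, so residual nerve block can be recorded as a longer spinal in some arms and not in others

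*Protocol*

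**What the plan says.** The outcome is defined twice in the Protocol, each time as the interval from the end of the intrathecal injection.

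- **In the ward:** the motor part runs "till recovery of the lower limbs motor power indicated by achieving grade 0 on modified bromage scale". The sensory part is "fine touch sensation indicated by sensing pin brick".
- **Collecting data** (last item before Statistical analysis): "offset of spinal anesthesia effect detected by degree 0 on modified bromage score and return of fine touch detected by sensing pin bricks".

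The scoring rule follows the section Administration of spinal anesthesia: "Patient is asked to elevate his extended lower limbs and the score is given as follows". The step that keeps a patient above grade 0 is "Grade 1 = Inability to raise extended leg; able to move knees and feet".

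Three other places decide what this rule captures.

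- **Inclusion criterion 7:** "Unilateral hip fracture assigned for surgical fixation". Each patient thus has one operated limb and one limb with no hip fracture.
- **Introductory text, on the fascia iliaca block:** "local anesthetic is injected between fascia iliaca and psoas muscle to block femoral, obturator and lateral cutaneous nerves". For PENG, the same text names the articular branches supplying the front of the hip capsule as the target.
- **Randomization:** groups P and F receive bupivacaine with magnesium on the fractured side before the spinal. Group C receives intravenous fentanyl and no block.

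**The concern.** An outcome called duration of spinal anesthesia should respond to the intrathecal drug and to nothing else that differs between the arms. The intrathecal dose is the same in all three groups, so a difference in this outcome would naturally be read as an effect of the block on the spinal.

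As defined, the outcome can also respond to the block directly. A patient whose spinal has worn off, but who cannot yet raise the operated leg or feel a pin on blocked skin, is still counted as under spinal anesthesia. Because the block is what was randomised, this error follows the treatment assignment. Randomisation and blinding do not remove it, since the definition itself creates it. At stake is a report that one block prolongs spinal anesthesia, or that PENG and fascia iliaca differ in this respect, when the data show only residual block.

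**Working it through.** The plan gives no figure for this outcome, so there is none to reproduce. The check is a comparison of the text, followed by arithmetic on assumed values.

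**Step 1. Which limb counts?** The motor wording is plural in the definition and in the scoring instruction, while grade 1 is worded for a single leg. Neither restricts the test to the non-operated limb, and no rule covers limbs that disagree. Reading the motor criterion as both limbs is natural. For pin-prick no side or dermatome is given, so the text shows only that blocked skin is not excluded.

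**Step 2. What does the operated limb carry in each arm?**

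| Group | Stated target on the fractured side | Injected volume of 0.25% bupivacaine | Bupivacaine |
|---|---|---|---|
| F | femoral, obturator, lateral cutaneous | 30 mL | 30 × 2.5 = 75 mg |
| P | articular branches to the hip capsule | 20 mL | 20 × 2.5 = 50 mg |
| C | none | none | none |

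Fracture and surgery are present in all three rows. The block is not.

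**Step 3. Is there a baseline that would separate block from spinal?** No Bromage grade or pin-prick result is called for between the block and the spinal. The only leg test in that interval is a passive 15-degree raise scored for pain, which does not measure active motor power.

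**Step 4. Form of the bias.** Let S be the true spinal offset and B the time at which block no longer prevents grade 0 or pin-prick in the operated limb, both counted from the intrathecal injection. If the operated limb is included, the recorded time is max(S, B). Then

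mean recorded − mean S = q × g,

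where q is the share of patients with B > S and g is their mean excess in hours. In group C the block contributes q = 0. If S has the same mean in all arms, the spurious differences due to block are

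- F versus C: q_F × g_F
- P versus C: q_P × g_P
- F versus P: q_F × g_F − q_P × g_P

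**Step 5. Illustration.** The documents give neither q nor g. The values below are assumptions chosen to show the range.

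| q | g = 1 h | g = 3 h | g = 6 h |
|---|---|---|---|
| 0.10 | 0.10 h | 0.30 h | 0.60 h |
| 0.25 | 0.25 h | 0.75 h | 1.50 h |
| 0.50 | 0.50 h | 1.50 h | 3.00 h |
| 0.75 | 0.75 h | 2.25 h | 4.50 h |

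The shift runs from negligible to several hours. Its direction is fixed: max(S, B) is never below S, so residual block can only lengthen the recorded time.

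**The case against.** The strongest reply has four parts.

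1. *The text never says both limbs, and a sensible assessor would use the sound leg.* The first half is right, and decisively so for pin-prick, where no site is stated. But the motor instruction is plural, and nothing directs the assessor to the sound leg. If some assessors do use it and others do not, the outcome also varies by assessor.

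2. *The protocol states no motor effect and no block duration.* This is correct. That a block outlasts the spinal in its effect on leg raise or skin sensation is inferred from the named target nerves. It limits what can be said about size, but does not show that the definition isolates the spinal.

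3. *Fracture and surgical pain affect everyone.* This stands. They mainly lengthen and blur the measure. They could differ by arm if pain relief differs, but the documents do not settle that. The block is the component that clearly differs by design.

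4. *The outcome is minor.* This also stands. It appears in none of the three objectives, nor in the hypotheses or the sample-size calculation.

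Two stronger readings are tempting and should be dropped. A reader might take the leg-raise test as proof that patients cannot lift the operated leg because of pain. The rule about intolerable pain belongs to the onset test, done after the block or fentanyl and before surgery, whereas spinal offset is read after fixation. A reader might also infer that some patients can never reach grade 0 within 24 hours. The 24-hour schedule is for vital signs and VAS, and no time limit is set for spinal offset.

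**Conclusion.** The concern holds in a limited form. The definition does not exclude the limb that carries the block, and the block differs by arm. Residual block can therefore be counted as spinal duration and bias this one between-group comparison. By stated target, group F is the most exposed, group P less clearly so, and group C not at all from a block.

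This rests on two assumptions: that the motor criterion is applied to both limbs or to the operated one, and that in some patients the block still affects leg raise or skin sensation when the spinal has worn off. The size cannot be derived from the documents. The 0.1 to 4.5 h in the illustration reflects assumed inputs only. A reader might infer a bias of a stated number of hours, or one that exceeds the spinal itself, but the documents support neither.

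Nor do the documents support reading this as a threat to the comparison of analgesia or to the sample size. It is a correction worth making to a secondary collected variable.

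**What to change.** Make three coordinated wording changes in the Protocol.

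1. **In the ward** and **Collecting data:** define offset of spinal anesthesia as modified Bromage grade 0 and return of pin-prick sensation in the non-operated limb, in all three groups.
2. **Modified Bromage scale, after Administration of spinal anesthesia:** add a note that, for the offset assessment only, the leg raise is scored in the non-operated limb. Without it, the instruction to raise both legs would conflict with the new definition. The use of the scale to judge readiness for surgery need not be touched.
3. **Optional:** record motor and sensory recovery of the operated limb as a separate variable, reported as a block outcome and not as spinal duration.

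Inclusion criterion 7 ensures that every patient has a non-operated limb. The cost is wording, plus one more recorded time if item 3 is adopted. The test is unchanged, items 1 and 2 add no procedure, and no treatment rule is affected.

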The statistical analysis will be performed using a Statistical Package for the Social Sciences (SPSS®) version 16 (SPSS Inc., Chicago, IL, USA) for windows 10 operating system. Quantitative data will be expressed as means \pm SD while Qualitative data will be expressed as numbers and percentages (%). A probability value (p-value) <0.05 is considered statistically significant.

Presentation of the statistical outcomes will be in the form of tables and graphs that will be performed using the “Microsoft Office Excel® 2013” program.

III. Administrative design:

- **Results:**

Collected data will be tabulated in tables and suitable graphs and analyzed according to standard statistical methods.

- **Discussions:**

Discussion will be done on results compared to related relevant literature and scientific researches.

- **Conclusion & Recommendations:**

They will be derived from the findings of the study.

References

1. **Parker M and Johansen A.** Hip fracture. *Bmj.* 2006;333(7557):27-30.
2. **Kowark A, Rossaint R and Coburn M.** General versus spinal anesthesia for the elderly hip fractured patient. *Current Opinion in Anesthesiology.* 2019;32(1):116-9.
7. **Helmerhorst GT, Vranceanu A-M, Vrahas M, Smith M and Ring D.** Risk factors for continued opioid use one to two months after surgery for musculoskeletal trauma. *JBJS.* 2014;96(6):495-9.
8. **Pasero C.** Fentanyl for acute pain management. *Journal of PeriAnesthesia Nursing.* 2005;20(4):279-84.

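### The mean ± SD rule does not suit time to first rescue, which has no value for a patient who never needs rescue; dropping such patients biases the comparison

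*Protocol*

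**What the plan says.** All references are to the Protocol.

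- **Summary rule (Statistical analysis).** "Quantitative data will be expressed as means" with SD. No variable is exempted. The threshold is given as "A probability value (p-value) <0.05 is considered statistically significant". No test is named; under Administrative design, Results, data are to be "analyzed according to standard statistical methods".
- **The variable (ward paragraph, and Collecting data).** "We will record time of first rescue analgesia", with the clock starting when the block or fentanyl injection is complete and stopping at the patient's first request. No value or censoring rule is given for a patient who makes no request.
- **When rescue is given (ward paragraph).** It is conditional on a VAS of at least 4, "or complains of intolerable pain, a rescue analgesia will be given in the form of nalbuphine". All groups also receive scheduled paracetamol and ketorolac.
- **Observation.** The last scheduled ward VAS is at 24 hours after surgery. The other 24-hour limit is attached to the amount of rescue drug: "total postoperative rescue analgesic consumption in first 24 hours postoperative".
- **Ambulation (Collecting data).** Defined as "time from end of surgery till first ambulation by the patient", with no stated end of observation.

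**The concern.** A patient who is never rescued has a time known only to exceed the period of observation. Such patients are foreseeable here, because rescue is conditional and is added to scheduled analgesia. A mean ± SD of this variable can be computed only by leaving them out or by assigning them a time. The Protocol fixes the summary and says nothing about which of the two would be done.

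Leaving them out is not a neutral loss of data, because they are the patients whose pain was best controlled. Objective 1 compares postoperative analgesic effect between the groups, and time to first rescue is one of the variables that describes how long the effect lasts. A comparison among rescued patients only is no longer a comparison of the randomised groups.

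**Working it through.** **Starting point.** The Protocol has no figure of its own for this variable. Its sample size rests on VAS at positioning for the spinal. The inputs are therefore:

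- 17 per group (Sample size);
- threshold 0.05 (Statistical analysis), taken as two-sided;
- 24 h window, borrowed from VAS recording and rescue consumption and, for simplicity, counted from injection (assumption);
- Weibull times, shape *k* of 1, 1.5 or 2, medians *m* of 8 vs 12, 10 vs 16 and 12 vs 20 h (assumptions, nine scenarios).

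**Formulas.** Scale λ = m / (ln 2)^(1/k); S(t) = exp[−(t/λ)^k]. Then:

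- true mean = λ Γ(1 + 1/k);
- unrescued share p = S(24);
- restricted mean R = area under S(t) from 0 to 24 h;
- mean among rescued patients only = (R − 24p) / (1 − p).

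If every unrescued patient is entered at 24 h, the ordinary mean is R.

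**One scenario in full: medians 10 vs 16 h, k = 1.5.**

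| | Shorter | Longer | Difference |
|---|---|---|---|
| λ (h) | 12.77 | 20.43 | |
| Unrescued share p | 0.076 | 0.280 | |
| True mean (h) | 11.53 | 18.44 | 6.9 |
| R, or unrescued entered at 24 h (h) | 11.10 | 15.45 | 4.35 |
| Rescued only (h) | (11.10 − 24×0.076)/0.924 = 10.04 | (15.45 − 24×0.280)/0.720 = 12.12 | 2.1 |

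Exclusion reports 2.1/4.35 = 48% of the restricted difference. Simulated power is about 13% for a t test on rescued patients, 38% for a t test with unrescued patients entered at 24 h, and 43% for the log-rank test.

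**All nine scenarios.**

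| | Range |
|---|---|
| Unrescued, shorter arm | 0-25% |
| Unrescued, longer arm | 6% to 43.5% (0.5^(24/20) = 0.435) |
| True difference | 4.3-11.5 h |
| Difference restricted to 24 h | 2.9-5.4 h |
| Difference, rescued only | 1.0-3.3 h |
| Power, t test, rescued only | about 5-44% |
| Power, t test, entered at 24 h | about 17-66% |
| Power, log-rank | about 20-75% |

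**Other shapes.** In 12 further scenarios (exponential, Weibull with shape 2, lognormal; means of 6-8 h vs 10-24 h), the rescued-only difference was always smaller than the true one, at 21-96% of it. The loss is small when few go unrescued: with 1% unrescued in the longer arm and Weibull means of 6 vs 10 h, exclusion gives 3.82 h instead of 4.00 h.

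**Is the direction certain?** Let rescued patients average 6 h in one arm and 12 h in the other, so the rescued-only difference is always 12 − 6 = 6.0 h. With unrescued patients counted to 24 h:

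| Unrescued (6 h arm, 12 h arm) | Difference to 24 h | Exclusion |
|---|---|---|
| 10%, 40% | (0.6×12 + 0.4×24) − (0.9×6 + 0.1×24) = 16.8 − 7.8 = 9.0 h | understates |
| 30%, 30% | (0.7×12 + 0.3×24) − (0.7×6 + 0.3×24) = 15.6 − 11.4 = 4.2 h | overstates |
| 40%, 10% | (0.9×12 + 0.1×24) − (0.6×6 + 0.4×24) = 13.2 − 13.2 = 0.0 h | overstates |

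The sign of the bias depends on where the unrescued patients are.

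**The case against.** **The sentence is a display rule, and the rest may be in a statistical analysis plan.** It names no test, and the choice of test is properly left open. What stands against this is that the summary itself is fixed for every quantitative variable, and for this one it cannot be computed as written once a patient goes unrescued. That is a poor choice in the text, not a missing detail.

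**The Protocol never says unrescued patients are excluded.** This is correct and limits the point. A reader might infer from the mean ± SD rule that power collapses. It does not follow: with unrescued patients entered at a common cut-off, the mean is the restricted mean, and power in the worked scenario is 38% against 43% for log-rank. The large loss belongs to exclusion alone, which is one of two ways of applying the rule.

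**Direction.** A reader might infer that the difference, in particular between PENG and fascia iliaca, is necessarily understated. The Protocol gives no rescue rates and no expected ordering of the two blocks, and the last table above shows that exclusion can also overstate.

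**The 24-hour window.** A reader might take it as part of this variable's definition. The wording "the first analgesia requested by the patient), total postoperative rescue analgesic consumption in first 24 hours" attaches it to consumption. The 24 hours also run from surgery, while the variable's clock starts at injection, before the spinal and an operation expected to last up to 3 hours. A one-clock window of 24 h therefore overstates censoring somewhat: at 24 + 3 = 27 h the unrescued share in the longer arm of the worked scenario falls from 28% to 22%.

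**Ambulation.** The same argument cannot simply be carried over. No end of observation is stated, so nothing in the text shows that any patient would lack a value.

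**Weight.** The sample size does not rest on this variable, and postoperative analgesia is also measured by repeated VAS and by rescue consumption, where an unrescued patient counts as an observed zero. This lowers the stakes but does not remove the problem.

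**Conclusion.** The point holds in a conditional form. The Protocol prescribes a mean ± SD for a variable that has no value in a foreseeable group of patients, and gives no rule for them. If they are dropped, the comparison is biased: towards a smaller difference when they are mainly in the longer-acting group, and possibly towards a larger one otherwise.

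The size is illustrative only. It rests on assumed Weibull times, an inferred 24 h window and 17 per group. On those assumptions exclusion gives about 1.0-3.3 h where the difference restricted to 24 h is 2.9-5.4 h. If almost every patient is rescued, the effect is slight. If unrescued patients are kept at a common cut-off, the restricted mean is recovered and little power is lost.

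The change should be made because the result should not depend on an unstated choice, and because it costs almost nothing. It is not fatal to the trial.

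**What to change.** In the Statistical analysis section:

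1. Exempt time to first rescue from the mean ± SD rule.
2. Censor patients without rescue at 24 h after surgery, or at last observation if earlier, with time still counted from the end of injection as the variable is defined. Censoring times will then differ a little between patients, which Kaplan-Meier methods handle.
3. Report Kaplan-Meier medians with 95% CI and a log-rank test. If a mean is wanted, report the restricted mean to one cut-off, counted from injection and common to all groups.
4. Report the number in each group who needed no rescue.
5. Treat time to ambulation in the same way only if some patients have not walked when observation ends.

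The cost is a sentence or two of text. No extra patients or measurements are needed beyond noting when observation of each patient ended, patient care is unchanged, and the methods are in standard software.
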